COMIRB Protocol

COLORADO MULTIPLE INSTITUTIONAL REVIEW BOARD
[name] [contact] [contact]

Project Title: Evaluation of Thyroid Stunning from a Diagnostic Dose of I-123

Principal Investigator: [name]

Version: 8.0 v. 7/26/2018

I. Hypotheses and Specific Aims:

Specific Aim: In a test-retest protocol, determine whether I-123 causes stunning.

Hypothesis: Pretreatment dosimetry with I-123 does not cause stunning of thyroid tissue and, therefore, does not reduce the benefit of subsequent therapeutic doses of I-131. Before I-123 can be used as the standard of comparison for other isotopes of radioiodine such as I-124, it must be proven that I-123 causes little or no stunning. We propose to address this question with the first prospective randomized intra-patient comparison of I-123 dosimetry by doing a I-123 imaging study twice, test-retest, before doing routine I-131 remnant ablation.

II. Background and Significance: The annual incidence of differentiated thyroid cancer in the United States is approximately 44,000 cases and the annual death rate is approximately 1,700 individuals (1). Although many patients do well with conventional therapy of surgery and remnant thyroid tissue ablation with I-131, a significant minority of patients develop regional and/or distant metastases. Initially, these metastases are differentiated and take up iodine and the standard of care is I-131 radioiodine therapy.

Currently, most hospitals treat patients with differentiated thyroid metastases with a fixed dose of 100 to 200 mCi of I-131 while a few university centers use individualized dosimetry to determine the maximum safe tolerable dose. The dosimetric approach is based on the assumption that a larger dose is more likely to ablate residual functioning thyroid cancer than a smaller dose. Although the dosimetric approach was described more than 45 years ago by Benua (2), there is still no consensus with respect to the advantage of the dosimetric approach over the fixed dose (3-9).

In the case of treatment with a fixed dose, the patient is usually treated with a therapeutic dose of I-131 without performing a preliminary biodistribution study. However, in the case of treatment with the maximum safe dose of I-131 based on dosimetry, it is necessary to give an initial small dose of radioiodine, usually I-131, to measure the biodistribution of radioiodine and in turn to calculate the maximum dose that the patient can safely tolerate. The dilemma is that there is significant, but controversial, evidence that the initial small dose of I-131 may stun the thyroid metastases and decrease the uptake of the subsequent therapeutic dose of I-131, thus defeating the purpose of dosimetrically determining the maximum safe dose (4,10-20).

The radioisotope of iodine, I-123, is a pure gamma emitter and is thought to be less likely to cause stunning than I-131. However, there are some reports that even I-123 can cause stunning (21-24).

If it is demonstrated that I-123 does not cause significant stunning, a follow-up separately funded prospective study can be designed to determine whether a dosimetrically determined dose of I-131 is superior to a fixed dose. If an individually calculated maximum dose is determined to be superior, it would suggest that the dosimetric approach, which is currently used in only a

small minority of patients, should be offered to all patients. This would represent a major advance in the treatment of patients with metastatic differentiated thyroid cancer. Alternatively, if a dosimetrically determined dose of I-131 is not superior to a fixed dose, all patients can be treated with the simpler less costly fixed dose regimen.

III. Preliminary Studies/Progress Report: N/A

IV. Research Methods

A. Outcome Measure(s): Difference in uptake of I-123 in the thyroid remnant in the neck in the two imaging studies. Greater than a 20% decrease from the first to second study will indicate evidence of stunning.

B. Description of Population to be Enrolled:

Inclusion criteria:

1. Patient must be 21-years-old or greater.
2. Patient must be status post near total thyroidectomy for differentiated thyroid cancer without known distant metastases and who are planning to undergo routine remnant thyroid tissue ablation with I-131.
3. Patients must qualify for thyroid ablation with I-131.

Exclusion criteria:

1. Women who are pregnant or breastfeeding.
2. Prior bovine TSH use.
3. Known metastatic thyroid cancer.
4. History of cardiovascular disease that may adversely affect patient participation at the discretion of the primary investigator.
5. Patients on hemodialysis.
6. Patients with acute serious illnesses at the discretion of the primary investigator.

C. Study Design and Research Methods: The proposed research will be the first study to perform test-retest studies in a group of patients to answer the long standing and fundamental question of whether diagnostic doses of I-123 cause stunning. Ten patients will be studied. If the patient elects to pursue participation in the study, the consent form will be explained to the patient

If the patient consents, the patient will undergo two I-123 whole body imaging studies prior to the I-131 thyroid remnant ablation.

Figure 1. General Scheme of Investigational Plan

The current standard of care is indicated in the solid black boxes and the additional research component is the dashed boxes.

[figure not shown]
[figure not shown]

Figure 2. Timing of standard of care and research interventions for the study population.

Patient Preparation

Participants will be placed on a low iodine diet for 1 week before the dosimetry study and continue on this diet until 24 hours after the therapeutic dose of ^{131}I .

Patient is prepared for the study by receiving an intramuscular injection of rhTSH (Thyrogen). The patients are prepared for receiving radioiodine by receiving an intramuscular injection of rhTSH (Thyrogen) on days 1, 2, 8, 9, 15 and 16 in order to raise the blood level of TSH and maximally stimulate the residual thyroid tissue to take up iodine (25-27). The Thyrogen received on days 1, 2, 8 and 9 will be provided free of charge by Genzyme. The subject's vital signs will be monitored before and after each Thyrogen injection. The Thyrogen injection will be withheld if vital signs show significant alterations from the patient's baseline.

Female patients of reproductive age who have not undergone a hysterectomy will undergo serum pregnancy tests on days 3 and 17 prior to administration of radioiodine.

All patients will have blood samples taken on days 3, 10, and 17 in the morning, to document that rhTSH was given and that there was a rise in thyroglobulin level (TSH action on thyroid cells) prior to administration of radioiodine.

Diagnostic imaging with I-123

On days 3 and 10 the patient is given 3 mCi of ^{123}I orally in the morning. The participant will be asked to fast at least 4 hours before and 1 hour after the I-123 oral dose to control for interference with I-123 uptake.

Imaging with gamma camera from the top of the head to the thighs is performed on days 4 and 11.

In each of the I-123 whole body diagnostic imaging studies, one done for research purposes and the other as routine care, a region of interest will be placed over the I-123 uptake in the residual thyroid tissue and the number of counts will be recorded (28). Less than a 20% decrease in counts from the first to the second study will be considered no significant stunning (29). The Null hypothesis is that there will be less than a 20% decrease in I-123 in the thyroid remnant from the first to the second study.

In order to more accurately measure I-123 uptake in the residual thyroid tissue from the I-123 whole body diagnostic image, an I-123 standard will be placed in the field of imaging at the time of image acquisition. Use of I-123 standard is common practice for calibrating I-123 activity in the body. By using an I-123 standard, in addition to recording the number of counts in the residual thyroid tissue and comparing the count differences between the first and second study, percent uptake of I-123 in the residual thyroid tissue can be calculated for each study and compared. Less than a 20% decrease in percent uptake of I-123 in the residual thyroid tissue will be considered no significant stunning and provide additional supportive data to measuring counts in the residual thyroid tissue.

If thyroid cancer metastases are incidentally discovered in the patient with no known metastases, the patient will be removed from the study and referred back to Endocrinology.

Thyroid tissue ablation with I-131

On day 17, the patient is given a fixed therapeutic dose of ^{131}I determined by the endocrinologist and nuclear medicine physician (range 30-100 mCi ^{131}I).

Post-treatment imaging evaluation

Approximately 7 to 10 days after therapeutic dose of radioiodine (day 23-26), patient returns for routine, standard of care post ^{131}I treatment imaging.

D. Description, Risks and Justification of Procedures and Data Collection Tools: A risk of participating in this research study is the relatively small additional radiation dose from second dosimetric study preceding the standard I-131 therapeutic ablation. Assuming a typical 30-100 mCi I-131 ablation dose, the one additional I-123 diagnostic study will increase the effective whole body dose by approximately 0.5%-1.6%. The small increase in radiation to the remnant thyroid tissue should be of no consequence since it will be ablated by the large therapeutic dose of I-131 one week later.

Another possible risk is that the radiation to the thyroid remnant from the initial experimental dosimetry studies will stun the remnant to the extent that it may not be effectively ablated. This is highly unlikely since the commonly used 30-100 mCi dose of I-131 is chosen for a significant margin of error so that very few remnants are not successfully ablated.

Patient Safety Monitoring Plan: Subject will remain in the clinical area for 20-30 minutes after each injection to be assessed for any acute adverse events. Symptoms will be recorded before and 20-30 minutes after injections. Subjects will be provided a primary phone number and an after-hours phone number to call with any questions or concerning symptoms. The most common reported side-effect symptoms are headache observed in 5% and nausea observed in 5% of patients. I-123 is a well-established FDA approved radiopharmaceutical used for diagnostic imaging of thyroid tissue and serious long term adverse events have not been reported. As a result, patients will be followed for potential adverse events until the completion of the routine standard of care treatment when the patient returns on days 23-26 for post-treatment imaging study.

The study Principle investigator, co-investigators and study coordinator will meet monthly to review preliminary data and discuss any safety related issues that may arise. The PI will be responsible for reporting any serious adverse events that are identified.

E. Potential Scientific Problems: None.

F. Data Analysis Plan: The primary endpoint will be measurement of thyroid remnant activity at 24 hours. We predict there will be less than a 20% reduction in the amount of I-123 in the thyroid remnant when the results of the second administered dose of I-123 is compared to the results from the first dose of I-123. The data will be analyzed statistically by the t-test and by the sign test. While we plan to study only 10 participants, this should be a sufficient number to determine whether there is any evidence of stunning by the sign test and, if there is stunning, whether there is more than a 20% stunning effect by the t-test. This is a pilot study, but it is likely to give results that are sufficiently definitive that it will not need to be repeated with larger numbers of participants. In addition, this is an internally funded research project that is intended to generate preliminary data to be

used in a larger NIH grant proposal that will compare fixed versus dosimetrically determined I-131 doses for treatment of patients with differentiated thyroid cancer with distant metastases.

G. Monitoring and Oversight

The sponsor investigator will be responsible for monitoring the trial per the trial monitoring plan, in addition to overseeing the safety and efficacy of the trial including any specimens collected, executing the data and safety monitoring (DSM) plan, and complying with all reporting requirements to local and federal authorities. This oversight will be accomplished through additional oversight from the Data and Safety Monitoring Committee (DSMC) at the University of Colorado Cancer Center (CU Cancer Center). The DSMC is responsible for ensuring data quality and study participant safety for all clinical studies at the CU Cancer Center, which is the coordinating institution of this trial. A summary of the DSMC's activities is as follows:

- Conduct of internal audits
- Ongoing review of all serious adverse events (SAEs), unanticipated problems (UAPs) and reportable adverse events (AEs)
- Has the authority to close and/or suspend trials for safety or trial conduct issues
- May submit recommendations for corrective actions to the CU Cancer Center's Executive Committee

Per the CU Cancer Center Institutional DSM Plan, SAEs, UAPs and reportable AEs are reported to the DSMC, IRB and the sponsor investigator per protocol. All SAEs, UAPs and reportable AEs are to be reported to the DSMC within 5 business days of the sponsor investigator receiving notification of the occurrence.

Each subject's treatment outcomes will be discussed by the site PI and appropriate staff at regularly scheduled meetings. Data regarding number of subjects, significant toxicities, dose modifications, and treatment responses will be discussed and documented in the meeting's minutes.

The sponsor investigator will provide a DSM report to the CU Cancer Center DSMC on a six month basis. The DSM report will include a protocol summary; current enrollment numbers; summary of toxicity data to include specific SAEs, UAPs and AEs; any dose modifications; all protocol deviations; and protocol amendments. The DSM report submitted to the DSMC will also include, if applicable, the results of any efficacy data analysis conducted. Results and recommendations from the review of this six month report by the DSMC will then be provided to the sponsor investigator in a DSMC review letter. The sponsor investigator is then responsible for ensuring this letter is submitted to the site's IRB of record at the time of IRB continuing review.

Quality Control and Quality Assurance

Site monitoring visits will be performed by the sponsor investigator's authorized representative on a regular basis, pursuant to the Monitoring Plan. During these visits, information recorded on the CRFs will be verified against source documents. Additional

computer programs that identify selected protocol deviations, out-of-range data, and other data errors within the electronic data entry may also be used to help monitor the study. As necessary, requests for data clarification or correction will be sent to the appropriate site PI.

Independent auditors from the sponsor investigator's authorized representative will be allowed by the site's PI to audit. In addition, audits may be conducted at any time by appropriate regulatory authorities and/or the IRB.

H. Summarize Knowledge to be Gained: There will be no benefits to the human subjects in this research project. However, there is likely to be significant benefit to future patients with differentiated thyroid cancer.

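### The day 10 I-123 dose has no pregnancy test of its own and relies on a result that is 7 days old

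*Combined protocol and SAP*

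**What the plan says.** Section IV.B excludes women who are pregnant or breastfeeding.

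Section IV.C sets three radioiodine administrations. Under its diagnostic imaging heading: "On days 3 and 10 the patient is given 3 mCi of ^{123}I orally in the morning". Under its ablation heading: "On day 17, the patient is given a fixed therapeutic dose" of I-131, in the range 30 to 100 mCi.

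Under Patient Preparation, female patients of reproductive age without a hysterectomy "will undergo serum pregnancy tests on days 3 and 17 prior to administration of radioiodine". The next paragraph adds a separate blood schedule: "All patients will have blood samples taken on days 3, 10, and 17 in the morning". Its stated purpose is to document that rhTSH was given and that thyroglobulin rose before radioiodine. Pregnancy testing is not among its purposes.

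Section IV.D describes the research risk as the "relatively small additional radiation dose from second dosimetric study preceding the standard I-131 therapeutic ablation". It says extra radiation to the remnant should not matter because "it will be ablated by the large therapeutic dose of I-131 one week later".

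**The concern.** The plan gives two of the three radioiodine doses a same-day serum pregnancy test and leaves the middle one without. A negative result on day 3 cannot show a pregnancy that becomes detectable only after that day. The plan accepts the value of rechecking, since it retests before the day 17 dose, but it does not say why day 10 is treated differently.

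What is at stake is exposing a woman who should by then be excluded to a diagnostic dose of radioiodine. If, as section IV.D suggests, the day 10 scan is the one added for research, that exposure would not be part of her routine care, and section IV.H states that participants gain no benefit from the research. No estimate, test or sample size in the study depends on this point.

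**Working it through.** No power or sample-size formula applies, and the plan states no figure to reproduce. The check compares two schedules.

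**Inputs**
- Radioiodine days: 3 and 10 (I-123, 3 mCi each) and 17 (I-131, 30 to 100 mCi), from section IV.C.
- Serum pregnancy test days: 3 and 17, from section IV.C, Patient Preparation.
- Blood draw days: 3, 10 and 17, before radioiodine, from the same heading.
- Sample size: "Ten patients will be studied", from section IV.C.

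**Step 1. Doses without a same-day test.** Dose days {3, 10, 17} minus test days {3, 17} leave {10}.

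**Step 2. Age of the latest scheduled test at each dose.**

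| Dose day | Agent | Latest test | Age of result |
|---|---|---|---|
| 3 | I-123, 3 mCi | Day 3 | 3 − 3 = 0 days |
| 10 | I-123, 3 mCi | Day 3 | 10 − 3 = 7 days |
| 17 | I-131, 30–100 mCi | Day 17 | 17 − 17 = 0 days |

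**Step 3. Does other text fill the gap?** The blood-sample sentence names day 10 and the pregnancy-test sentence does not, so the test schedule cannot be read as covering day 10 by implication. Nothing else in the visible text provides a test between days 3 and 17 or a contraception rule.

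**Step 4. Which I-123 study is the research one?** Section IV.C says one is research and the other routine care, without saying which. Section IV.D refers to the second study and places I-131 a week after it. Since 17 − 10 = 7 days, this points to day 10. It is an inference, and steps 1 to 3 do not depend on it.

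**Step 5. Size of the exposure.** The day 10 activity is 3/100 = 3% to 3/30 = 10% of the I-131 activity, but these are different isotopes, so the ratio is not a dose comparison. Section IV.D puts one added I-123 study at about 0.5% to 1.6% of the effective whole body dose. That is a figure for the patient, not for a fetus. Neither number measures fetal risk, and the documents give none that does.

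**Step 6. Number affected.** The protocol does not say how many participants will be women who need testing. Taking the full range of 0 to 10 of the ten patients, 0 to 10 day 10 doses are affected. At two tests each the current total is 0 to 20; at three tests each it would be 0 to 30. The difference is 0 to 10 assays.

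**The case against.** The strongest reply is that the omission may be deliberate. The protocol never promises a test before every dose. It sets the two schedules in adjacent paragraphs and gives them different days, and testing at entry and again before the much larger I-131 dose is a coherent approach. Nothing in the documents says that a 7-day-old negative serum test is inadequate. This stands in part: it is why the point is a gap in a design choice and not an error. It does not supply the missing reason for treating day 10 differently.

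A second reply is that Figure 2, which shows the timing of interventions, or the consent form may include a day 10 test or a contraception instruction. That cannot be excluded, because neither was available. If one of them does, the sentence in section IV.C still needs to be brought into line.

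A third is that the research scan is not clearly the day 10 scan. Section IV.D also speaks of the initial experimental dosimetry studies in the plural, and Thyrogen is supplied free for both I-123 studies, so funding does not separate them. This weakens the argument about added research exposure. The main point is unaffected: day 10 is a radioiodine dose without a current test under either reading.

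Finally, the risk is small. That is accepted. A cheap fix does not make the gap more serious, but it does make leaving the gap open hard to justify.

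**Conclusion.** The concern holds. On the visible text, one of three radioiodine doses, the 3 mCi of I-123 on day 10, is given on a pregnancy result that is 7 days old, against 0 days for the other two. The finding about the written schedule is firm. It is limited by the absence of the timing figure and the consent pages. The number of women affected is unknown and is taken as 0 to 10 of ten.

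The absolute risk is small, and there is no effect on the primary endpoint, the sample size or the planned tests. The change should be made because it protects against an excluded condition at very little cost, not because the study's conclusions are in doubt.

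**What to change.** In section IV.C, Patient Preparation, change the pregnancy-test days from 3 and 17 to 3, 10 and 17, keeping the same eligible group and the requirement that the test come before radioiodine. State that the day 10 assay uses the blood already drawn that morning and that the I-123 dose is held until the result is known. This is the sequence already implied on day 3, where a serum test comes before a morning dose. Check that Figure 2 and the consent form agree.

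If waiting for the result delays the day 10 dose, time the day 11 imaging from the actual dose, so that the 24-hour measurement named as the primary endpoint in section IV.F is kept and the two scans remain comparable.

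The cost is one edited sentence, one more assay per eligible woman (0 to 10 in total) and possibly a short wait on day 10. No visit or blood draw is added. After the change, the age of the test result at the second I-123 dose falls from 7 days to 0.

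### The protocol neither masks the person placing the regions of interest to scan order nor requires matched regions on a patient's two scans, so a reading difference could not be told apart from stunning or its absence

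*Combined protocol and SAP*

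**What the plan says.** Section IV.C (Diagnostic imaging with I-123) defines the measurement: in each study "a region of interest will be placed over the I-123 uptake in the residual thyroid tissue and the number of counts will be recorded". The two scans are "one done for research purposes and the other as routine care", and their timing is the same for everyone: "Imaging with gamma camera from the top of the head to the thighs is performed on days 4 and 11".

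The counts are judged against a 20% cut. IV.C says: "Less than a 20% decrease in counts from the first to the second study will be considered no significant stunning". IV.A gives the other side: "Greater than a 20% decrease from the first to second study will indicate evidence of stunning". IV.F states the expected answer: "We predict there will be less than a 20% reduction in the amount of I-123 in the thyroid remnant".

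IV.C adds a calibration step, in which "an I-123 standard will be placed in the field of imaging at the time of image acquisition". This gives percent uptake as supportive data.

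The protocol does not say who places the region, whether it is drawn by hand or by software, how its edge or background is set, whether there is a second read, or whether the reader knows which scan came first. Section IV.E lists no potential scientific problems.

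**The concern.** Scan order cannot be varied, because stunning by the first dose can only be seen on a later scan. There is also no group that has a second scan without an earlier I-123 dose. The estimated change in each patient therefore contains any stunning plus any systematic difference in how the two regions were placed, and no planned analysis can separate them. Control over the reading is the safeguard that remains, and the protocol does not describe any.

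The team has declared which side of the cut it expects, so a reader who knows the order could be influenced without intending it. IV.F also expects the result to be definitive enough not to need repeating, so calling the study a pilot does not remove the need for a protected measurement.

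**Working it through.** **Inputs from the protocol:** 10 patients; two scans each, in fixed order; a 20% cut; a t-test for more than 20% stunning and a sign test for any stunning (IV.F). No alpha, sidedness, SD or power is given, so there is no sample-size calculation to reproduce. The point does not depend on one.

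**Assumptions, not in the protocol:** log-normal error; within-patient scan CV 10% (15% in brackets); the 20% cut applied to the group geometric mean; one-sided 5% t-test on the log ratio; a reading shift *b*, meaning that second-scan regions collect a fraction *b* more counts in every patient.

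**1. Shift that moves a true fall *d* to exactly 20%:** *b* = 0.80/(1 − *d*) − 1.
- *d* = 22%: 0.80/0.78 − 1 = 2.6%
- *d* = 25%: 0.80/0.75 − 1 = 6.7%
- *d* = 30%: 0.80/0.70 − 1 = 14.3%

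**2. Apparent fall:** 1 − (1 − *d*)(1 + *b*). For *d* = 25%, *b* = 5% gives 1 − 0.75 × 1.05 = 21.25%, and *b* = 10% gives 1 − 0.75 × 1.10 = 17.5%. A shift the other way exaggerates stunning: with 5% fewer counts, a true 20% fall reads as 1 − 0.80 × 0.95 = 24%.

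**3. Chance that the observed group fall is under 20%.** The mean log ratio has SE = √(2 ln(1 + CV²)/10) = 0.0446 (0.0667). The chance is 1 − Φ(z), with z = [ln 0.80 − ln((1 − *d*)(1 + *b*))]/SE. For *d* = 25%, *b* = 5%, CV 10%: z = (−0.2231 + 0.2389)/0.0446 = 0.353, giving 36%.

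| True fall | b = 0 | b = 5% | b = 10% |
|---|---|---|---|
| 25% | 7% (17%) | 36% (41%) | 75% (68%) |
| 35% | under 0.1% (0.1%) | under 0.1% (0.9%) | 0.6% (5%) |

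At a true 10% fall, unbiased reading already gives a result under 20% in more than 99% (96%) of trials, so an upward shift changes little there.

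**4. Power of the t-test that IV.F describes.** Noncentrality is [ln((1 − *d*)(1 + *b*)) − ln 0.80]/SE with 9 df, and the test rejects below −1.833. At *d* = 30%:
- *b* = 0: noncentrality −2.99 (−2.00), power 87% (58%)
- *b* = 5%: noncentrality −1.90 (−1.27), power 54% (32%)

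**5. A second model.** Take the percent change as normal with an assumed SD of 10%, 20% or 30%. At a true 25% fall, the chance that the mean reads under 20% for *b* = 0, 5% and 10% is 6%, 35%, 79% (SD 10%); 21%, 42%, 65% (SD 20%); and 30%, 45%, 60% (SD 30%). The pattern is the same, and weaker as noise grows.

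**6. The I-123 standard.** Percent uptake is remnant counts scaled by the standard. If second-scan remnant counts are multiplied by (1 + *b*), so is second-scan percent uptake, and the ratio between scans shifts equally. The standard corrects for differences in camera sensitivity, not for region placement.

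**The case against.** A reader might infer that unmasked staff draw the regions by hand on dated images and tilt them towards the predicted result. The documents do not support that. IV.C names no operator, does not say how the region is formed and does not describe image labels. It cites a reference at this step (28) that cannot be checked here and may describe a method. The protocol is silent; it does not state open reading. Silence nevertheless leaves unmasked, unmatched reading permitted.

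The monthly team meetings might also be cited as evidence of exposure to results. The sentence, "will meet monthly to review preliminary data and discuss any safety related issues", belongs to the Patient Safety Monitoring Plan. It does not say that region counts are shown or that the person placing regions attends, so little weight should rest on it.

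A reader might further conclude that a 5% shift raises a false finding of less than 20% stunning, at a true 20% fall, from 5% to 26% (17%). The arithmetic is right for a test in that direction, but it is not the planned test. IV.C makes less than 20% the null hypothesis, and IV.F uses the t-test to show more than 20%. For that test the same shift lowers the false-positive rate, from 5% to about 0.4% (1.0%). The harm is lost power.

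Finally, the CVs and the size, direction and consistency of the shift are all assumed, and nothing shows that the true fall lies near the cut. That stands, and it limits the claim to a risk.

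**Conclusion.** The concern holds as a gap in the measurement plan. The only primary measurement rests on regions whose placement is neither masked to scan order nor matched within patient, in a fixed-order design without a control group. Any systematic reading difference enters the estimated change in full, and the I-123 standard does not remove it.

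No bias has been demonstrated. On the assumptions above, shifts of about 3% to 7% are enough to carry true falls of 22% to 25% across the cut, while a true 35% fall is rarely hidden even by a 10% shift. The safeguard costs little and protects the trial's one key number, so this is a cheap improvement and not a fatal flaw.

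**What to change.** In IV.C, state that for the research endpoint:
- regions are placed only after both of a patient's scans are complete;
- the images are stripped of date and scan order and presented in random order;
- region size and shape are the same on both scans of a patient, as is the background region if background is subtracted.

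The protocol should also say who places the regions and by what rule. Clinical reading of the scans, including for incidental metastases, proceeds as usual.

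The cost is a few sentences and the relabelling of 20 images (10 patients × 2 scans), with no extra visit, radiation or patient. There are two downsides. Research quantification waits for the second scan. Masking is also only partial if the same person has already read the scans clinically; a reader without that role would be better where one is available. No sample-size figure changes.

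### The null hypothesis is the conclusion the trial wants to prove, and a finding of no significant stunning needs no confidence limit

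*Combined protocol and SAP*

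**What the plan says.** Section I (Hypotheses and Specific Aims) sets the burden of proof. Before I-123 can serve as the comparison standard for other radioiodines, "it must be proven that I-123 causes little or no stunning". The Data Analysis Plan (IV.F) states the expected result: "We predict there will be less than a 20% reduction in the amount of I-123 in the thyroid remnant".

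Section IV.C, under diagnostic imaging with I-123, then makes that expected result the null: "The Null hypothesis is that there will be less than a 20% decrease in I-123 in the thyroid remnant". The same paragraph gives the decision rule: "Less than a 20% decrease in counts from the first to the second study will be considered no significant stunning". Percent uptake is judged by a rule of the same form, as supportive data. Section IV.A gives the mirror rule: "Greater than a 20% decrease from the first to second study will indicate evidence of stunning".

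On the tests, IV.F says: "The data will be analyzed statistically by the t-test and by the sign test". It gives the sign test the question of any stunning. The t-test is to show, "if there is stunning, whether there is more than a 20% stunning effect by the t-test". No alpha, sidedness, confidence interval, equivalence test or non-inferiority test is stated. IV.F calls the study a pilot but expects it to be "likely to give results that are sufficiently definitive that it will not need to be repeated with larger numbers of participants".

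**The concern.** A significance test can reject its null hypothesis but cannot prove it. Here the claim to be proven is assumed true unless the data overturn it, so ten noisy pairs of scans would tend to leave it standing. The decision rule does not repair this, because it looks at the observed decrease alone. An observed decrease just under 20% counts as no significant stunning however wide the uncertainty around it.

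The favourable conclusion is the trial's only aim. It is meant to qualify I-123 as a reference isotope, and sections II and H make it the condition for a follow-on trial of dosimetric against fixed I-131 dosing. A false clearance would carry into that trial.

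A smaller point is the order of testing. IV.F can be read as testing the 20% margin only after a positive sign test, yet it also says without condition that both tests will be done. Under either reading, no test is set up to reject in favour of a decrease below 20%.

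**Working it through.** **Inputs from the documents.** Ten patients, each scanned twice (IV.C, IV.F); a margin of a 20% decrease (IV.A, IV.C). Alpha, power, SD and expected change are not given, and section III reports no preliminary data. The sample size of 10 therefore cannot be reproduced.

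**Assumptions.** Within-patient percent change is normal with SD 15, 20 or 30 percentage points; one-sided alpha is 5%; the 20% rule applies to the group mean. Write δ for the true mean decrease. The t critical value on 9 df is 1.833.

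**1. The written rule (observed mean decrease below 20%).** P(favourable) = Φ((20 − δ)/(SD/√10)). Example: δ = 25, SD = 20 gives SE = 20/3.162 = 6.32, z = −5/6.32 = −0.79, probability 0.215.

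| True decrease | SD 15 | SD 20 | SD 30 |
|---|---|---|---|
| 20% | 50% | 50% | 50% |
| 25% | 15% | 21% | 30% |
| 30% | 2% | 6% | 15% |

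Beyond the margin, more noise makes the hoped-for answer more likely.

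**2. The t-test in the stated direction (reject if the decrease is significantly above 20%).** This is a noncentral t with 9 df and noncentrality (δ − 20)√10/SD. At δ = 30 and SD = 20 the noncentrality is 10 × 3.162/20 = 1.58. The chance of not rejecting at a true 30% decrease is 38%, 57% or 75% at SD 15, 20 or 30. Failure to reject therefore says little.

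**3. The sign test.** Eight decreases out of 10 give one-sided p = 56/1024 = 0.055; nine give 11/1024 = 0.011 (two-sided 0.021). Nine are needed either way. Each patient shows a decrease with probability Φ(δ/SD). The chance of a non-significant result is:

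| True decrease | SD 15 | SD 20 | SD 30 |
|---|---|---|---|
| 20% | 23% | 49% | 76% |
| 25% | 8% | 29% | 63% |
| 30% | 2% | 14% | 49% |

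These are rates of non-significance only. The plan does not say that a non-significant sign test means no stunning.

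**4. The reversed test (favourable only if mean + 1.833 × s/√10 is below 20).**

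| True decrease | SD 15 | SD 20 | SD 30 |
|---|---|---|---|
| 30% (false pass) | <0.5% | <0.5% | <0.5% |
| 25% (false pass) | 0.4% | 0.9% | 1.6% |
| 20% (false pass) | 5% | 5% | 5% |
| 10% (correct pass) | 62% | 43% | 25% |
| 0% (correct pass) | 99% | 90% | 62% |

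If the sample SD is 15, 20 or 30, the half-width 1.833 × SD/√10 is 8.7, 11.6 or 17.4 points. The observed mean decrease must then be below 11.3%, 8.4% or 2.6%.

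**5. Patients needed for 80% power with the reversed test, one-sided 5%.** With no true change: 6, 8 or 16. With a true 10% decrease: 16, 27 or 58.

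**The case against.** The strongest reply is that IV.F promises a t-test with a 20% comparison and states no sidedness. A two-sided test against 20% would also reject when the mean decrease is significantly below 20%, which is the evidence needed. But the text does not say this. IV.F names only an effect above 20%, and the null in IV.C points the same way. If the other direction was intended, the plan has to say so.

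Second, the documents do not say whether 20% applies to the group mean or to each patient. On a per-patient reading the rates in step 1 do not apply. That stands as a limit on the figures, but a per-patient rule would have no group-level error rate either.

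Third, the 50% figure belongs to any point-estimate cutoff evaluated at its own cutoff. That is true; the 25% and 30% rows are more informative.

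Fourth, this is a pilot, and no enrolled patient's treatment depends on the test. The pilot label would carry more weight if IV.F did not expect results firm enough to make repetition unnecessary, and if section I did not ask for proof.

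Fifth, every size rests on an assumed SD. That is so. The fault in the hypotheses does not depend on it.

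**Conclusion.** The concern holds. The stated null is the desired conclusion, neither planned test can reject in its favour as described, and the only rule for reaching it ignores sampling error. Following the plan as written can therefore give an unsupported clearance of I-123. This must be corrected because it affects the trial's sole aim.

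On the stated assumptions, the written rule clears a true 25% decrease in 15% to 30% of trials, against 0.4% to 1.6% with a confidence-limit rule. The logical defect is certain. The sizes depend on the assumed SDs, normality and the group-mean reading.

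The fault lies in the planned analysis, not in the paired design. The same ten pairs could support the claim if variability is modest and the true change is near zero: at one-sided 5%, 80% power with no true change requires an SD of about 23.5 points or less.

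**What to change.** Amend IV.A, IV.C and IV.F as follows.

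- State H0: the mean decrease is 20% or more; H1: the mean decrease is less than 20%.
- Make the primary analysis a one-sample t-test of the within-patient percent change against the 20% margin, at a stated one-sided alpha (for example 5%), run whatever the sign test shows.
- Conclude no significant stunning only if the one-sided 95% upper confidence limit of the mean decrease is below 20%. Conclude stunning above 20% only if the one-sided 95% lower limit is above 20%. Otherwise report the result as inconclusive.
- Report the sign test as supportive.
- Say that the 20% margin applies to the group mean, and name the measure tested. IV.C already makes percent uptake supportive to counts.
- State the assumed SD and the resulting power at 10 patients.

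A log-ratio analysis with margin 0.80 is an option, not a requirement. With log SD 0.15, 0.20 or 0.30 its power with no true change is 99.6%, 94.5% or 70.0%.

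The change is rewording and needs no new measurements. Its cost is more inconclusive results. At SD 30, power with 10 patients is only about 62% even with no true change, and 25% if the true decrease is 10%. A stricter one-sided 2.5% level would need 7, 10 or 20 patients for 80% power with no true change at SD 15, 20 or 30. If the SD may be near 30, either the sample size or the expectation of a definitive result has to be reconsidered.
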